6.2 Timing of evaluations

6.2.1 Screening Evaluations

Screening evaluations must occur prior to the participant starting any study medications, treatments, or interventions. Screening evaluations to determine eligibility must be completed within 14 days prior to study entry unless otherwise specified. For participants from whom informed consent has been obtained but who are deemed ineligible or who do not enroll into the study, they will be logged as a screening failure. Participants who meet the enrollment criteria will be randomized to the study.

6.2.2 Entry Evaluations

Entry evaluations must occur within 14 days of the first screening evaluation unless otherwise specified. Participants should begin treatment ideally on the day of but at most 24 *hours* after randomization.

6.2.3 Discontinuation Evaluations

Evaluations for Randomized Participants Who Do Not Start Study Treatment

All CRFs must be completed and keyed for the period up to and including the entry visit. Participants who do not start study treatment will be taken off study with no further evaluations required.

Premature Treatment Discontinuation Evaluations

Participants who prematurely discontinue study treatment permanently will have premature discontinuation evaluations performed as noted in Section 6.1 as soon as possible after stopping study treatment, but no later than 14 days after stopping treatment. If the participant discontinues treatment prematurely, the participant will be encouraged to continue on study and receive all evaluations per 6.1 Schedule of Events.

Premature Study Discontinuation Evaluations

Participants who prematurely discontinue participation in the study should have the premature study discontinuation evaluations noted in Section 6.1 performed as soon as possible.

Evaluations for Participants Who Die

All CRFs must be completed and keyed for the period up to the week of death.

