2.4 SECONDARY ENDPOINTS

1. Proportion of participants with Grade 3 or higher AEs at 4 weeks

2. Proportion of participants who complete LZD treatment

3. Exposure-response (PK-PD) relationship, with LZD as predictor and Grade 3 or higher AE as outcome variable

4. Modified Rankin Scale (death, severe disability, moderately severe, moderate disability, slight disability, no significant disability, no symptoms) at 12 and 24 weeks

5. Montreal Cognitive Assessment (MoCA) or neurocognitive battery performance at 12 and 24 weeks

6. Exposure-response (PK-PD) relationship, with linezolid as predictor and Modified Rankin Scale as outcome variable

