3.3 Late exclusion (exclusion after enrollment)

1. Confirmed drug-resistant MTB infection: Resistance testing will be performed on all *M. tuberculosis* isolates from cerebrospinal fluid or other specimens obtained prior to randomization. If a participant is confirmed to have drug resistant infection, defined as resistance to one or more first-line TB medications or linezolid, they will be excluded from the study. If drug resistance is confirmed through phenotypic susceptibility testing, results may not become available until after a participant is enrolled, at which point they would meet criteria for late exclusion.

2. Identification of an alternative cause of meningitis: If CSF or other laboratory or pathology results return after a participant is enrolled indicating an alternative (or secondary) cause of meningitis, they would meet criteria for late exclusion.

Participants who meet criteria for late exclusion will discontinue study treatment but remain on study. These participants will be replaced in order to maintain a balanced number of participants per arm.

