4.1.7 Randomization

At study entry and prior to the 4th dose of TB treatment, participants will first be randomized by a computer-generated permutated block randomization (block size of 2 or 4) with a 1:1 randomization to high (35 mg/kg) versus standard dose (10 mg/kg) rifampicin. A second 1:1 randomization will then be performed to linezolid 1200 mg daily or no linezolid. Randomization will be stratified by British Medical Research Council (BMRC) TBM disease grade (Table 2), determined at the time of consent, given the association between worse disease severity and higher mortality¹.

Table 2. British Medical Research Council (BMRC) TBM disease grade

GRADE I	Glasgow coma score 15, no focal neurological signs
GRADE II	Glasgow coma score 11–14 with or without focal neurological sign or Glasgow coma score 15 with focal neurological signs
GRADE III	Glasgow coma score \leq 10 with or without focal neurological signs

The randomization schedules will be provided to the site pharmacy in a listed sequence. The sequential, unique randomization code will be recorded on the study entry CRF to assure there is no

skipping of the randomization order. All randomized participants will initiate their allocated study TB treatment within 24 hours of randomization and ideally the same day. For participants from whom informed consent has been obtained, but who are deemed ineligible or who do not enroll into the protocol, a Screening Failure form must be completed and entered into the database.

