9.0 CRITERIA FOR DISCONTINUATION

9.1 Permanent and Premature Treatment Discontinuation

- Drug toxicity that is possibly, probably or definitely related to high-dose rifampicin or linezolid, and that requires permanent discontinuation of any of these drugs
- Confirmed drug-resistant MTB infection
- Another infection cause found that is not MTB
- Sustained non-adherence that, in the opinion of the investigator, warrants early discontinuation.
- Requirement for prohibited concomitant medications.
- Pregnancy or breastfeeding.
- Request by participant or next of kin/caregiver to terminate treatment.
- Clinical reasons believed life threatening by the physician, even if not addressed in the toxicity section of the protocol

Participation is entirely voluntary so participants may choose to discontinue the trial treatment at any point without penalty. Participants should be encouraged to remain in the trial for the purpose of follow-up and data analysis. Where study drug is discontinued or the dose is modified it should be recorded in the follow-up CRF.

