9.2 Premature Study Discontinuation

- Request of a medical provider or investigator if they think the study is no longer in the best interest of the participant.
- The participant or next of kin/caregiver refuses further follow-up evaluations (i.e., withdraws continued consent to participate).
- At the discretion of the IRB and other regulatory authorities as part of their duties to ensure that research participants are protected, or the industry supporter or its designee.

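### Sections 6.2.3 and 9.2 allow consenting randomised participants to leave follow-up after open-label allocation, so Week 12 and 24 Rankin and vital-status data may be lost from the secondary linezolid comparison

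*Combined protocol and SAP*

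**What the plan says.** Section 6.2.3 has a rule for people who are randomised but never dosed: "Participants who do not start study treatment will be taken off study with no further evaluations required". Section 9.2 lists, as a reason to end study participation and not only treatment: "Request of a medical provider or investigator if they think the study is no longer in the best interest of the participant". Withdrawal of consent is a separate bullet in 9.2, so this reason covers people who still consent.

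Elsewhere the protocol keeps people under observation. For those who start and then stop, 6.2.3 says "the participant will be encouraged to continue on study and receive all evaluations per 6.1 Schedule of Events". Section 9.1 says "Participants should be encouraged to remain in the trial for the purpose of follow-up and data analysis", and 8.1.6 keeps people on study after temporary or permanent drug discontinuation. Section 3.3 goes further: "Participants who meet criteria for late exclusion will discontinue study treatment but remain on study". For those who leave the study, 6.2.3 asks for an exit assessment: "Participants who prematurely discontinue participation in the study should have the premature study discontinuation evaluations noted in Section 6.1 performed as soon as possible".

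The outcome at issue is secondary endpoint 4 in Section 2.4: "Modified Rankin Scale (death, severe disability, moderately severe, moderate disability, slight disability, no significant disability, no symptoms) at 12 and 24 weeks". Secondary objective 3 (Section 2.3) compares functional outcomes between participants randomised to linezolid and to no linezolid. Section 4.0 states that the trial is open label. On timing, 4.1.7 says: "All randomized participants will initiate their allocated study TB treatment within 24 hours of randomization and ideally the same day". Section 10.2 gives no analysis method, analysis population or missing-data rule for the Rankin score.

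**The concern.** A randomised comparison is protected only if people are kept or dropped for reasons unrelated to their allocation. Here both exits operate once allocation is known. Someone who takes one dose and stops is to be encouraged to stay to Week 24, while someone who takes none is dropped, and the protocol gives no reason for the difference.

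The arms also differ in what there is to start. The fixed-dose tablets come from routine care (5.2), and a participant may already have taken up to three doses of TB treatment at randomisation (4.1.7). Arm D adds nothing to that backbone. Arms A and B add linezolid, and Arms A and C add extra rifampicin. If declining an added drug counts as not starting, non-starting is more likely outside Arm D. What is at stake is the Week 12 and 24 Rankin comparison, in which death is the worst category. Outcomes that were never collected may not be recoverable at analysis.

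**Working it through.** **The plan's own figures.** The plan gives no power, dropout rate or non-starter rate for the Rankin comparison. Its only between-arm power statement (10.1) is for myelosuppression: 40% versus 10%, 30 per arm, at least 80%. An exact calculation for the uncorrected chi-square test gives 79.6%, and the normal approximation gives 78.0%. That is close to the stated figure, but it has no bearing on this point.

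**Who can be lost, and what is still recorded.**

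| Situation | Recorded | Not assured |
|---|---|---|
| Dies before first dose | Death, as an SAE (7.3, 7.4, 7.7); CRFs to week of death (6.2.3) | Inclusion in the analysis (10.2 silent) |
| Alive, never starts | CRFs through entry | Vital status and Rankin at Weeks 12 and 24 |
| Leaves under 9.2 | One exit Rankin (Table 5, early-withdrawal column) | Weeks 12 and 24 |
| Starts, then stops | Encouraged to continue all scheduled visits | - |

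The second row is the main gap. Section 7.3 ends expedited reporting when a participant is discontinued from the study. Section 7.7 ties the end of SAE notification to the last protocol dose, which a non-starter does not have. A later death in that row need not reach the database.

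**Effect on observed mortality.** Inputs: 30 on linezolid and 30 not (10.1); mortality about 40% (7.4, no time horizon given), taken as equal in both groups, so 0.40 × 30 = 12 deaths in each. The number lost from one group, k, is my assumption.

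- If all k lost would have died, observed mortality is (12 - k)/(30 - k).
- If none of the k would have died, it is 12/(30 - k).

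| k | All would have died | Shift (points) | None would have died | Shift (points) |
|---|---|---|---|---|
| 0 | 12/30 = 40.0% | 0 | 12/30 = 40.0% | 0 |
| 1 | 11/29 = 37.9% | -2.1 | 12/29 = 41.4% | +1.4 |
| 2 | 10/28 = 35.7% | -4.3 | 12/28 = 42.9% | +2.9 |
| 3 | 9/27 = 33.3% | -6.7 | 12/27 = 44.4% | +4.4 |

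If the loss is the same in number and prognosis in both groups, the difference is zero. For example, two deaths lost from each gives 10/28 against 10/28. Loss unrelated to outcome also gives no bias on average.

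**Effect on a test.** For an uncorrected chi-square test on death with true mortality 40% in both groups, exact enumeration gives a false-positive rate of 4.9% at k = 0. Under the one-sided case where all k would have died, with the reduced group treated as binomial at its lowered rate, it is 5.8% at k = 1, 6.6% at k = 2 and 8.3% at k = 3. Depending on how the loss is modelled, the k = 3 figure is about 8 to 10%.

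**The case against.** The strongest reply is that very few people can fall through. Dosing is due within 24 hours of randomisation and Day 1 is defined as the first day of study drug (4.1.2). Participants are inpatients for the first two weeks (6.3.4). Deaths in that gap are reportable and settle the Rankin category. The wording is the same for all arms. Arm C, a no-linezolid arm, also carries an added drug, so the comparator can lose people too. The term study treatment is itself unclear: 5.0 and Table 3 use it for the whole regimen in all four arms, while 8.0 speaks of study-provided drugs. On the first reading, a person taking the backbone who declines linezolid has started and stays on study. The primary PK endpoint needs dosed participants and is not harmed. A best-interest exit from the study is also a different category from stopping treatment, so 9.2 does not strictly contradict 9.1.

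All of this stands, and it limits the point. A reader might infer that the trial will lose participants selectively by arm, or that the loss will favour linezolid because the sickest disappear. The documents support neither. They give no count of non-starters, the earliest deaths are largely captured, and losing people who would have survived reverses the sign. What the reply does not remove is the written rule that living, consenting randomised participants have no later outcome collected. Nothing in Section 10 makes up for that.

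**Conclusion.** The point holds as a weakness in the rules, not as a demonstrated bias. Sections 6.2.3 and 9.2 permit post-allocation, possibly arm-related loss of Week 12 and 24 Rankin and vital-status data from a secondary randomised comparison. The gap concerns mainly living non-starters and, to a lesser degree, provider-initiated exits, who have one exit Rankin score.

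Size and direction are unknown. Each person lost from one 30-person arm shifts that arm's observed mortality by about -2.1 to +1.4 points, assuming 40% mortality in both arms and loss from one arm only. One or two losses would matter little. Three, all of whom would have died and all from one arm, would give a false difference of 6.7 points, but nothing in the documents makes that likely. I rate this a cheap improvement, not a must-fix.

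**What to change.** - **6.2.3:** Keep randomised non-starters on study, without PK sampling or PK lumbar punctures. Collect vital status and Modified Rankin Scale at Weeks 12 and 24, and Grade 3 or higher AEs through Week 4 to match secondary endpoint 1, unless consent to follow-up is withdrawn. The meaning of starting then no longer decides who is followed.
- **9.2:** Limit a provider's or investigator's request to ending study treatment or study procedures. Still collect vital status and Rankin at Weeks 12 and 24, by visit or telephone, unless the participant or proxy withdraws consent to follow-up.
- **10.2:** State that the Rankin comparison includes all randomised participants in their allocated arm.

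The cost is protocol wording and a few extra contacts for a handful of participants. No new procedure is needed, and the primary PK analysis does not change.

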Cumulative toxicity is less of a concern when adjunctive LZD is administered for a short duration.³²⁻³⁴ LZD's narrow therapeutic window has tempered the enthusiasm for its therapeutic utility for TB. While most treatment-limiting toxicities, including myelosuppression, gastrointestinal (GI) symptoms and optic neuropathy, are reversible, some, including a painful, sensory-predominant neuropathy, may be permanent.^{35,36} LZD toxicity is driven by both dose and duration.³⁷ In 796 patients with gram-positive bacterial infections on LZD 600 mg BID, hematologic toxicities correlated with treatment duration, occurring in 5% of patients on LZD for 2 to 4 weeks. Peripheral neuropathy occurred in only 3 individuals with a mean treatment duration of 95 days.³⁸ Among 85 patients with DR TB on LZD, the majority of AEs occurred after 2 months.³³ Of 33 patients on LZD 1200 mg for XDR TB, anemia and GI symptoms were common (~50%) but necessitated discontinuation in only 2 patients within the first month.³⁹ No cases of peripheral or optic neuropathy occurred before 2 months. We will use a short course of adjunctive LZD, which has not been studied in a randomized trial for TBM, early in intensive therapy to augment bactericidal activity during the logarithmic growth phase of TB while minimizing cumulative toxicity.

Linezolid and the CSF compartment

CSF to plasma concentration ratios of 0.6 to >0.9 support good to excellent CNS penetration of LZD. However, the distribution of LZD in the CSF, from small studies of mostly neurosurgical patients, varies substantially. After a one-time dose of LZD 600 mg IV, mean CSF maximum concentrations (C_{max}) ranged from 5.1 to 6.6 ug/mL. At steady state, CSF C_{max} was 1.3 to 7.1 and up to 10.8 µg/mL, and minimum concentrations (C_{min}) were <0.2 to 3.1 and up to 6.1 µg/mL. The ability to achieve adequate CSF concentrations for sufficient duration has been inconsistent. One study found CSF LZD concentrations were >4 µg/mL for the entire dosing interval, while in another few patients reached concentrations >1 µg/mL. The minimum inhibitory concentration for 90% of isolates (MIC₉₀) is generally <0.5 µg/mL.

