6.3.4 Assessment of adherence

Participants will be hospitalized for the first 2 weeks of therapy, during which directly observed therapy will occur. After 2 weeks, participants can be discharged at the discretion of the inpatient physician. Once discharged, adherence will be assessed at in-person follow up visits by self-report (or by proxy report) and pill counts. Study staff will also endeavor to contact participants weekly by phone for remotely observed therapy.

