6.3.14 Lumbar Puncture

Lumbar puncture (LP) will be performed as per section 6.1. Prior to LP, participants must have platelets ≥50,000 cells/mm³ measured within 72 hours prior to the LP and no contraindication to LP per the treating clinician. Opening pressure in the lateral decubitus position will be measured by manometry, when possible, and recorded. CSF cell count, glucose, protein, and AFB smear and culture will be performed. Repeat lumbar puncture must be performed if AFB culture and/or Xpert Ultra are not performed on the CSF obtained during routine care used for screening.

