6.3.20 Storage of biospecimens

Blood and CSF specimens will be stored from consenting participants. Specimens collected for storage will be labeled with study identification number and collection date, and will not be labeled with participant name. Specimens will be stored at the site and shipped in batches to the US-based team for testing. Additionally, samples should be collected a) if failure or relapse is suspected and the participant is evaluated at an unscheduled or sick visit or b) if a participant voluntarily withdraws from the study. Participant consent for collection and storage of specimens will be part of the study consent

form which will be administered during the entry visit, with an independent signature line.

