10.2 Planned analyses

The primary outcomes will be CSF and plasma LZD PK parameters, including CSF to plasma ratio, rate of CSF uptake, and plasma absorption rate constant (k_a), drug clearance (Cl/F), volume of distribution (V_d). We will employ a model-based approach using non-linear mixed effects modeling in NONMEM to estimate plasma and CSF PK parameters based on simultaneous analysis of all plasma and CSF drug concentration data.⁷⁴ We will perform post-hoc Bayesian predictions of secondary LZD PK parameters, including C_{max} , time to C_{max} , AUC₀₋₂₄, and elimination half-life in plasma and in CSF. Based on this approach, we will characterize the dynamic uptake of LZD in the CSF when administered with high and standard dose RIF over 4 weeks and derive a dosing algorithm for LZD to achieve target exposures through simulations. Pharmacodynamic breakpoints for LZD against TB are not established, but we will use target AUC₀₋₂₄, AUC/MIC, T>MIC for LZD of 160 µg*hr/mL, 100, and 85%, respectively.^{23,75,76} We will use sparse sampling to estimate the AUC curve based on CSF sampling early, at steady state, and before LZD discontinuation.⁷⁷

For the LZD adverse event evaluation, the primary outcome will be a dichotomous measure of Grade 3 or higher (yes/no) myelosuppression (e.g., anemia, thrombocytopenia, leukopenia) during the 4 weeks of therapy. A secondary outcome will be LZD discontinuation or dose reduction (yes/no) for any AE. We will compare the frequency of myelosuppression between the LZD and no LZD arms across RIF dosing with the Cochran-Mantel-Haenszel test, which accounts for stratified randomization. Within

the LZD arm, we will explore differences in the frequency of myelosuppression between the standard and two high dose RIF arms combined by a chi-square test. We will use an exposure-response model using logistic regression to test if the probability of myelosuppression and LZD discontinuation is related to PK measurements, including C_{min} , C_{max} and AUC₀₋₂₄.

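### A participant who leaves the study between Weeks 2 and 4 has no required blood count in the later part of the window for the myelosuppression outcome

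*Combined protocol and SAP*

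**What the plan says.** Table 5 (Section 6.1) schedules hematology without condition at screening, entry, Week 1, Week 2 and Week 4. Entry may be deferred if screening results are recent. Nothing is scheduled at Week 3 or from Week 8 on. In the sick-visit and early-withdrawal columns, hematology depends on there being an indication. The early-withdrawal column does require, unconditionally, symptom assessment, a targeted exam, the neuropathy screen, vision and neurocognitive testing, the PHQ-9, the Modified Rankin Scale and stored plasma.

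Section 6.2.3 brings that column into force for study leavers: "Participants who prematurely discontinue participation in the study should have the premature study discontinuation evaluations noted in Section 6.1 performed as soon as possible". For a participant who only stops treatment, it asks for the discontinuation evaluations and adds that "the participant will be encouraged to continue on study and receive all evaluations per 6.1 Schedule of Events". Section 8.1.6 likewise keeps such participants on study to completion.

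On the outcome, Section 10.2 says that for the linezolid adverse-event evaluation "the primary outcome will be a dichotomous measure of Grade 3 or higher (yes/no) myelosuppression", assessed over the 4 weeks of therapy. On timing, Section 1.0 reports that in one series "hematologic toxicities correlated with treatment duration, occurring in 5% of patients on LZD for 2 to 4 weeks". On setting, Section 6.3.4 says: "After 2 weeks, participants can be discharged at the discretion of the inpatient physician".

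**The concern.** The adverse-event comparison depends on a laboratory result, and a low count can be silent. A participant who leaves after the Week 2 visit may have taken further linezolid, as an outpatient, in the part of the course where Section 1.0 places hematologic toxicity. Blood is due at withdrawal for storage, but the test behind the outcome is optional.

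Two things are at stake. First, the outcome is incompletely observed for these participants, and Section 10 does not say whether someone without a late count is scored as a non-event, excluded or imputed. Second, whether a count is done rests on judgment in an open-label trial. Section 4.0 promises only an effort to blind the staff who assess adverse events, so testing could differ between linezolid and no-linezolid participants. Analysis cannot recover a count that was never taken.

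Leaving in this window is foreseeable without any toxicity. Section 4.1.5 allows surrogate consent, says altered mental status may be present in more than 50% of patients, and withdraws anyone who regains capacity and declines to continue.

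**Working it through.** **1. Counts required of a Week 2 to 4 study leaver.** Week 2 has a window of ±2 days, so the last required count can fall on Day 12. Required counts after that: none. Up to about 28 − 12 = 16 of the 28 treatment days are then without a required count.

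**2. Whether another section closes the gap.**
- Section 6.3.14 requires platelets "measured within 72 hours prior to the LP". That covers platelets only and depends on a lumbar puncture, which is itself conditional at early withdrawal.
- The repeat counts in Section 8.1.2 start only once an abnormal count has been found.
- Section 7.6 does not treat asymptomatic laboratory abnormalities as reportable events unless listed conditions are met, so it gives little prompt to test a symptom-free leaver.
- Section 6.3.13 records every post-entry laboratory value regardless of grade, but only if the test was done.

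None of these requires a full count.

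**3. The plan's power figure.** Inputs from Section 10.1: 40% against 10%, 30 per arm, significance level 0.05 (two-sided assumed), stated power at least 80%.
- Unpooled normal approximation: standard error √(0.24/30 + 0.09/30) = √0.011 = 0.1049; 0.30/0.1049 − 1.96 = 0.90; power 81.6%.
- Arcsine approximation: 80.3%.
- Exact enumeration of two binomials with the uncorrected chi-square test: 79.6%.
- Pooled normal approximation: 78.0%. Fisher's exact test: 70.5%.

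The stated figure reproduces to within rounding by the first three methods. The exact chi-square value, 0.796, is the base below. It uses a single 2×2 table and ignores the stratification in the planned Cochran-Mantel-Haenszel test.

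**4. Illustrative effect of missing late counts.** Three assumptions are not in the documents: k untested leavers in each arm of 30; a leaver without a late count is scored as a non-event; a share s of events would arise only after the Week 2 count. The observed rate in each arm is then p × (1 − s·k/30).

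| k per arm | s | Linezolid rate | No-linezolid rate | Power |
|---|---|---|---|---|
| 0 | – | 40.0% | 10.0% | 0.796 |
| 1 | 0.5 | 39.3% | 9.8% | 0.787 |
| 2 | 0.5 | 38.7% | 9.7% | 0.777 |
| 3 | 0.5 | 38.0% | 9.5% | 0.767 |
| 1 | 1 | 38.7% | 9.7% | 0.777 |
| 2 | 1 | 37.3% | 9.3% | 0.757 |
| 3 | 1 | 36.0% | 9.0% | 0.736 |

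For example, with k = 3 and s = 1: 0.40 × (1 − 3/30) = 0.36 and 0.10 × (1 − 3/30) = 0.09.

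**5. If leavers are excluded instead.** With 3 per arm gone (27 per arm), the unpooled approximation falls from 81.6% to 77.4% and the pooled one from 78.0% to 73.4%. The order of size is the same.

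**The case against.** The strongest defence is that the gap is narrow. Section 9.1 lists drug toxicity as a reason to stop treatment; Section 9.2, on leaving the study, does not. Participants with recognised toxicity are therefore the ones the plan keeps on schedule with a Week 4 count due, and Section 8.1.6 adds laboratory follow-up when toxicity stops study therapy. The Week 1 and Week 2 counts capture earlier events. The trial's primary endpoints are pharmacokinetic, and this comparison serves a secondary safety objective. All of that stands, and it limits the severity.

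A required count would also not reach everyone. Some leavers will be refusing further evaluations. Stored samples need separate consent (Section 6.3.20). The plan expects about 40% of participants to die of TBM, and deaths before Week 4 are unaffected by this change. That stands too.

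A reader might go further than the documents allow in four ways.
- That everyone who stops linezolid loses the later count. Section 6.2.3 says otherwise.
- That leavers are mainly those with intolerance, so that the loss is selective. Nothing in the documents shows this.
- That power could fall to about 0.50. That figure (0.499) requires three leavers, all in the linezolid arm, each with an undetected event and scored as a non-event, with no credit for the Week 1 and 2 counts.
- That a leaver gets no safety check. The column still requires a symptom review and targeted exam, and it permits a count.

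What the defence does not answer is the core point: no section requires a count for a participant who leaves the study between Weeks 2 and 4.

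**Conclusion.** The point holds for participants who leave the study after the Week 2 count and before Week 4. They can have no blood count in the later part of the outcome window, and whether they do is discretionary. A count may still be done if indicated or in routine care, so this is a gap in what is required and not proof that data will be missing.

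Under the stated assumptions the loss of power is about 1 to 3 percentage points if half of events come after Week 2, and about 2 to 6 points if all do. The true size cannot be derived, because the documents give neither a withdrawal rate nor a scoring rule for missing counts.

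It is tempting to conclude that the comparison is biased for or against linezolid. The documents do not support either direction: selective testing of linezolid leavers would push the contrast one way, untested leavers the other, and blinding of adverse-event assessors is at least intended. This is a cheap improvement of minor severity.

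**What to change.** In the early-withdrawal column of Table 5, make hematology required in all four arms for anyone who leaves the study before the Week 4 visit, and at the discontinuation evaluation for anyone who stops study drug before Week 4. Keep it conditional after Week 4. Draw it with the stored-plasma sample where consent allows. State in Section 10.2 that the result counts toward the Week 0 to 4 myelosuppression outcome.

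The cost is one table cell, one sentence, and routine counts for a few participants. Sample size, significance level and planned power do not change. Some leavers will decline the test, and the change does nothing for participants who die before Week 4.
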